2.1.4.2 Deaths

The death observation periods are per the observation periods defined above.

- Death pre-treatment: death occurring during the pre-treatment observation period
- Death on-study: death occurring during the on-study observation period
- Death on-treatment: death occurring during the on-treatment observation period

Death poststudy is death occurring after the last protocol planned visit and before database lock for LTS16004.

2.1.4.3 *Laboratory safety variables*

Clinical laboratory data consists of blood analysis, including hematology and clinical chemistry, and urinalysis. Clinical laboratory values after conversion will be analyzed in standard international units and international units will be used in all listings and tables. Baseline for laboratory variables is baseline from DRI15928.

Blood samples for clinical laboratories will be obtained according to the SoA, protocol Section 1.3, unless otherwise specified. The laboratory parameters are detailed in the protocol Section 10.2.

2.1.4.4 *Vital signs variables*

Vital signs include body temperature (degrees Celsius), heart rate (beats/minute), respiratory rate (breaths/minute), and systolic and diastolic blood pressure (mmHg). Blood pressure and heart rate measurements will be assessed consistently in sitting or supine position. The baseline for vital signs is the baseline from DRI15928.

2.1.4.5 *Electrocardiogram variables*

Single 12-lead ECGs will be obtained using an ECG machine that automatically calculates ECG parameters: heart rate, PR, QRS, QT, and QTc. Due to differences in ECG between DRI15928 and LTS16004, the LTS16004 Day 1 ECG will be used as baseline.

2.1.4.6 *Columbia suicide severity rating scale*

The C-SSRS is a tool used to assess the lifetime suicidality of a participant and to track suicidal events throughout the study. The structured interview prompts recollection of suicidal ideation, including the intensity of the ideation, behavior and attempts with actual/potential lethality.

The scale is administered by the Investigator or a qualified designee at the time points indicated in the protocol SoA (protocol Section 1.3).

The C-SSRS categories have binary responses (yes, no):

- Category 1 - Wish to be dead
- Category 2 - Non-specific active suicidal thoughts
- Category 3 - Active suicidal ideation with any methods (not plan) without intent to act
- Category 4 - Active suicidal ideation with some intent to act, without specific plan
- Category 5 - Active suicidal ideation with specific plan and intent
- Category 6 - Preparatory acts or behavior
- Category 7 - Aborted attempt
- Category 8 - Interrupted attempt
- Category 9 - Actual attempt (non-fatal)

Category 10 - Suicidal behavior

Composite endpoints are defined as:

Suicidal ideation - a “yes” answer at any time during treatment to any 1 of the 5 suicidal ideation questions (Categories 1-5)

Suicidal behavior - a “yes” answer at any time during treatment to any 1 of the 5 suicidal behavior questions (Categories 6-10)

Suicidal ideation or behavior - a “yes” answer at any time during treatment to any 1 of the 10 suicidal and behavior questions (Categories 1-10)

2.1.5 PD endpoints

The following exploratory endpoints will be assessed in LTS16004.

- [REDACTED] in case of index AEs (cytopenia and arrhythmias).
- [REDACTED]

2.2 DISPOSITION OF PARTICIPANTS

Screened participants in LTS16004 are people who signed the informed consent form. Screen failures are defined as participants who consent to participate in the LTS16004 study but cannot continue due to eligibility criteria.

For participant study status, the total number of participants for each one of the following categories will be presented in the clinical study report using a summary table and/or flow chart diagram:

- Screened/Randomized participants in DRI15928
- Participants who completed the planned study treatment period as per protocol in DRI15928

LTS16004:

- Screened participants
- Screen failure participants according to reason, if available
- Enrolled participants
- Treated participants
- For Part A, participants who completed treatment and those who permanently discontinued by main reason
- For Part A, participants who completed the study period, and those who ended the study period prematurely by main reason

- For Part B, participants who completed treatment and those who permanently discontinued treatment by main reason
- For Part B, participants who completed the study period and those who ended the study period prematurely by main reason

For interim assessment of disposition, those ongoing on treatment and/or study will also be included.

For all categories of participants (except for screened/randomized in DRI15928, completed treatment in DRI15928 and screened categories in LTS16004) percentages will be calculated using the number of enrolled participants in the LTS16004 study as the denominator. A listing of participants who discontinued treatment will include the treatment the participant was receiving at the time of discontinuation. A separate listing of reasons for study discontinuation will be provided.

A participant is considered lost to follow-up at the end of the study if he/she is not assessed at the last protocol planned visit and is unable to be contacted by the study site.

Additionally, the analysis populations for safety and efficacy ([Section 2.3](#)) will be summarized in a table by number of participants on the enrolled population.

Data will be presented for the following tolebrutinib dose groups: 5/60, 15/60, 30/60, and 60/60 mg, and all.

2.2.1 Protocol deviations

The number and percentage of participants with a critical or major protocol deviation will be summarized by deviation and overall, within dose group. A by participant listing of all critical and major deviations will be provided.

2.3 ANALYSIS POPULATIONS

2.3.1 Efficacy population

mITT population: defined as all participants enrolled in LTS16004 who have at least 1 day of IMP exposure during the study. All participants will be summarized in the dose group to which they were randomized in DRI15928 and overall.

2.3.2 Safety population

Safety population: all participants enrolled in LTS16004 and exposed to IMP during LTS16004, regardless of the amount of exposure.

2.4 STATISTICAL METHODS

Continuous data will be summarized using the number of available data, mean, SD, median, minimum, Q1, Q3, and maximum for each dose group. Categorical and ordinal data will be summarized using the number and percentage of participants in each dose group.

P-values will not be calculated.

2.4.1 Demographics and baseline characteristics

Only participants enrolled in LTS16004 will be summarized on demographic and baseline characteristic data. Parameters described in [Section 2.1.1](#) will be summarized by the tolebrutinib dose group and overall using descriptive statistics.

Medical and surgical history data will be summarized by SOC and PT. Events are sorted by SOC internationally agreed order and by decreasing frequency of PT based on incidence in the overall tolebrutinib group.

2.4.2 Prior and Concomitant medications

Prior and concomitant medication will be summarized by dose group and overall, only for the participants enrolled into LTS16004. Medications will be summarized according to the WHO-DD dictionary, considering the first digit of the anatomic category (ATC) class (anatomic category) and the first 3 digits of the ATC class (therapeutic category). All ATC codes corresponding to a medication will be summarized, and participants will be counted once in each ATC category (anatomic or therapeutic) linked to the medication. Therefore, participants may be counted several times for the same medication.

The table for prior medications will be sorted by decreasing frequency of anatomic category followed by all other therapeutic classes based on the overall incidence across dose groups. In case of equal frequency regarding anatomic categories (respectively therapeutic categories), alphabetical order will be used.

The tables for concomitant medications will be sorted by decreasing frequency of anatomic category followed by all other therapeutic classes based on the incidence in the overall group. In case of equal frequency regarding anatomic categories (respectively therapeutic categories), alphabetical order will be used.

In addition, the systemic corticosteroid treatment for MS relapse will be analyzed by number and percentage of confirmed relapse requiring steroid treatment. These medications will be summarized by ATC code and standardized medication name.

2.4.3 Extent of investigational medicinal product exposure and compliance

2.4.3.1 Extent of investigational medicinal product exposure for tolebrutinib

The extent of IMP exposure will be assessed by the duration of IMP exposure in LTS16004.

Duration of IMP exposure is defined as last dose date in LTS16004 - first dose date in LTS16004 + 1 day, regardless of unplanned intermittent discontinuations. Exposure will be summarized for the study as a whole and separately for Parts A and B. Part A exposure will be summarized according to tolebrutinib dose group (5, 15, 30, and 60 mg).

Overall duration of IMP exposure will be summarized descriptively as a quantitative variable (number, mean, SD, median, minimum, and maximum). In addition, duration of IMP exposure will be summarized categorically by counts and percentages for each of the following categories and cumulatively according to these categories:

- $0 < \text{Duration} \leq 24$ weeks
- $24 < \text{Duration} \leq 48$ weeks
- $48 < \text{Duration} \leq 72$ weeks
- $72 < \text{Duration} \leq 96$ weeks
- $96 < \text{Duration} \leq 120$ weeks
- $120 < \text{Duration} \leq 144$ weeks
- $144 < \text{Duration} \leq 168$ weeks
- $168 < \text{Duration} \leq 192$ weeks
- $192 < \text{Duration} \leq 216$ weeks
- $216 < \text{Duration} \leq 240$ weeks
- Duration ≥ 240 weeks.

For Part A exposure, 12-week intervals will be used.

Additionally for each exposure summary, the cumulative duration of treatment exposure will be provided, defined as the sum of the duration of treatment exposure for all participants, and will be expressed in participant years.

2.4.3.2 Compliance

Compliance data will be summarized by tolebrutinib dose group and overall, only for the LTS16004 participants in the safety population. A given administration will be considered noncompliant if the participant did not take the planned dose of treatment as required by the protocol. No imputation will be made for participants with missing or incomplete data.

Percentage of compliance for a participant will be defined as the number of administrations that the participant was compliant divided by the total number of administrations that the participant was planned to take from the first to the last administration.

Treatment compliance percentages will be summarized descriptively as a quantitative variable (number, mean, SD, median, minimum, and maximum). The percentage of participants who have a compliance of <80% will also be summarized.

Cases of symptomatic overdose, as mentioned in protocol Section 8.3.1, will be listed as AESIs. Dosing irregularities categorized as critical or major protocol deviations will be listed (Section 2.2.1).

2.4.4 Analysis of efficacy endpoints

The primary objective of this LTS16004 study is to evaluate safety. Efficacy data will be summarized with appropriate measures of variability.

For by visit summaries including data from DRI15928, visits during the DRI15928 period correspond to weeks on tolebrutinib treatment.

MRI variables

Number and volume of lesions will be summarized by visit using descriptive statistics in the mITT population including data from both DRI15928 and LTS16004. For parameters with a baseline value, change and/or percent change from baseline will be included. For new/enlarging T2 lesions, the values will be standardized to per month values by dividing by the number of months (4-week intervals) from the previous MRI to the current MRI. In addition, average number of lesions per scan (new Gd-enhancing T1 hyperintense and new T1 non-enhancing hypointense) or annualized rate of lesions (new/enlarging T2) will be summarized descriptively. Graphical presentations may be used to illustrate trends over time.

Values for Gd-enhancing T1 lesions will be excluded if the participant had a suspected MS relapse and was receiving systemic corticosteroids within the 30 days prior to the MRI assessment date given the short-term effects of systemic corticosteroids on Gd-enhancing lesions.

Listings of MTR recovery and number of phase rim lesions will be provided.

For each dose group and overall, the percentage of participants with no new MRI disease activity will be provided by visit.

Time course of intensity related parameters and MTR recovery will be modeled using generalized linear mixed modeling. Annualized brain volume loss will be modeled as well.

Annualized MS relapse rate

A gross estimate of ARR is the total number of relapses for participants by dose group divided by the sum of the standardized study duration for participants in the dose group.

Total number of confirmed relapses and standardized study duration will be calculated for each participant as:

- Total number of confirmed relapses is defined as number of confirmed relapses with onset between first IMP date and treatment discontinuation/completion date (same as last dose intake date) in LTS16004.
- Standardized study duration (in years) will be calculated by $(\text{last dose intake date} - \text{first IMP date} + 1) / 365.25$ in LTS16004.

ARR will be analyzed using a negative binomial regression model in the mITT population. The model will include the total number of confirmed relapses with onset between first and last IMP doses in LTS16004 as response variable and dose group (5/60, 15/60, 30/60, and 60/60 mg) as covariate. Log transformed standardized treatment duration will be included in the model as an "offset" variable. The estimated ARR for each dose group and corresponding 95% 2-sided CI will be derived from the negative binomial model. The relative reductions in ARR (60/60 mg versus each other dose group) along with 95% CIs will be estimated from the model.

Number of participants with 0, 1, 2, 3, 4, or ≥ 5 relapses will be presented by dose group, namely, 5/60, 15/60, 30/60, and 60/60 mg.

The ARR for the tolebrutinib 60 mg treatment period will be analyzed using a negative binomial regression model, as well. Only relapses with onset during the tolebrutinib 60 mg treatment period will be counted, which means Part B only for participants originally assigned to 5, 15 and 30 mg dose groups and Parts A and B for participants originally assigned to the 60 mg dose group. Excluded are patient years and relapses during the first 8 weeks of tolebrutinib treatment after the switch to Part B for participants in the 5/15/30 to 60 mg groups and the same for participants in the 60/60 mg dose group, if the sum of the placebo run-out period (if applicable) and any gap period is >4 weeks. The negative binomial regression model will use total number of relapses as the response variable and log transformed standardized treatment duration as an "offset" variable. The estimated ARR and the 95% CI will be provided.

The number of participants with 0, 1, 2, 3, 4, or ≥ 5 relapses during the tolebrutinib 60 mg treatment period will also be presented.

Proportion of participants relapse free

Time to first confirmed relapse in LTS16004 is defined as "the date of first relapse - first IMP date (in LTS16004) + 1". If the participant has no relapse before treatment discontinuation/completion, then the participant will be considered as free of relapse until the date of treatment discontinuation/completion. His/her data will be censored after this date. The proportion of participants without confirmed relapse in LTS16004 will be estimated based on the Kaplan-Meier curve at yearly time points (1, 2, 3, 4 and 5 years since first IMP in LTS16004).

Change from baseline in EDSS scores

Change from baseline in EDSS scores will be summarized by tolebrutinib dose group and overall using descriptive statistics. Only EDSS scores on scheduled visits will be used for the analysis to exclude the temporary fluctuations in the clinical status that may occur with a relapse.

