3 OBJECTIVES AND ENDPOINTS

Table 6 - Objectives and endpoints

Objectives	Endpoints
Primary	

To determine the long-term safety and tolerability of SAR442168 in RMS participants	Adverse events (AEs), serious adverse events (SAEs), safety findings on magnetic resonance imaging (MRI), potentially clinically significant abnormalities (PCSA) in laboratory tests, electrocardiogram (ECG), or vital signs during the study period.
Secondary	
To evaluate efficacy of SAR442168 on disease activity, assessed by clinical and imaging methods.Number of new gadolinium (Gd)-enhancing T1-hyperintense lesions by brain MRI.Number of new or enlarging T2 lesions.Total number of Gd-enhancing T1-hyperintense lesions.Number of relapses (annualized relapse rate [ARR]) during the study period.Change in Expanded Disability Status Scale (EDSS) score from baseline over time.
Tertiary/exploratory To evaluate efficacy of SAR442168 on disease activity and the pharmacodynamics (PD) of SAR442168.	
[REDACTED] in case of index AEs (cytopenia and arrhythmias).[REDACTED][REDACTED]Change in volume of T2-lesions from baseline over time.Change in brain volume, including regional changes, over time.Change in the number of T1-hypointense lesions from Baseline over time.Change in myelin integrity and other features of MRI lesions as measured by magnetization transfer ratio and susceptibility-weighted imaging MRI over time.Proportion of participants with no new MRI disease activity through the end of the study.Proportion of relapse-free participants through the end of the study.[REDACTED][REDACTED]

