8.1 EFFICACY ASSESSMENTS

8.1.1 Magnetic resonance imaging assessments

Cranial (brain) MRI with and without Gd contrast will be performed. Basic MRIs will be performed for all participants at all study sites and will consist of T2- and T1-weighted sequences without and with Gd contrast.

Due to a potential safety risk related to deposition of certain IV Gd contrast agents in the brain, these agents should be used in accordance with local recommendations/regulations ([20](#)).

The study manual containing instructions for standard image acquisition requirements for brain MRI, data transfer to the central review center, archiving, and shipping will be provided to all participating sites. Study site personnel will undergo training regarding MRI acquisition and data handling procedures, training will be documented, and adherence to the manual will be monitored throughout the study with retraining performed as necessary.

Number of new and total number of T1 Gd-enhancing hyperintense as well as new/enlarging T2 lesions will be evaluated at the visits specified in the SoA ([Section 1.3](#)), comparing lesion count to that from the previous MRI scan.

Unless specified otherwise, the baseline brain MRI will be used as the reference to assess all MRI derived endpoints. The last MRI obtained in the DRI15928 study, if performed within 6 weeks prior to Day 1 of the LTS16004 study, will be acceptable as the baseline MRI for this study. Standardized endpoint evaluation will be assured by central review of brain MRI scans. Blinded central review will be performed for all MRI-derived endpoints. In Part A, MRI reviewers will be blinded to treatment assignments and to other participant data. In Part B, MRI reviewers will not be blinded. Details on MRI testing and central review will be described in the study manual.

Spinal MRIs may be required if spine MS lesions are suspected by the Investigator. Spinal MRIs will be evaluated locally and reported in the eCRF. No central review will be performed for spinal MRIs.

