2.1.3.1 MRI parameters

For MRI parameters, data from both DRI15928 and LTS16004 will be examined. The last MRI obtained in the DRI15928 study, if performed within 6 weeks prior to Day 1 of the LTS16004 study, will be acceptable as the Day 1 MRI for the LTS16004 study.

MRI assessment will be performed at visits as specified in the protocol [Section 1.3](#) SoA.

MRI parameters include:

- Number of new Gd-enhancing T1 hyperintense lesions (secondary)
- Number of new or enlarging T2 lesions (secondary)
- Total number of Gd-enhancing T1-hyperintense lesions (secondary)
- Volume of T2 and new/enlarging T2 lesions (tertiary/exploratory)
- Number of new T1 non-enhancing (hypointense) lesions (tertiary/exploratory)
- Volume of T1 non-enhancing (hypointense) lesions (tertiary/exploratory)
- Percent change from baseline in sum of brain volume (tertiary/exploratory)
- Percent change from baseline in sum of thalamus volume (tertiary/exploratory)

- Percent change from baseline in sum of cerebral cortex volume (tertiary/exploratory)
- Change in myelin integrity and other features of MRI lesions as measured by magnetization transfer ratio (MTR) and susceptibility-weighted imaging MRI (tertiary/exploratory):
 - Number of slowly enlarging lesions
 - Volume of slowly enlarging lesions
 - Number of phase rim lesions
 - MTR recovery in Gd-enhancing lesions
- Proportion of participants with no new MRI disease activity through the end of the study defined as 0 new Gd-enhancing T1-hyperintense lesions and 0 new or enlarging T2 lesions. (tertiary/exploratory)
- Normalized T1 intensity evolution in slowly evolving lesions
- Normalized T1 intensity evolution in screening unenhancing T2 lesions
- Normalized T1 intensity evolution in phase rim regions of interest

In the DRI15928 study and the LTS16004 study Part A the central reader is blinded and in the LTS16004 study Part B the central reader is not blinded.

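### New T1-hypointense lesion counts are not adjusted for the time between MRIs, unlike new/enlarging T2 counts, so widening scan gaps can produce a false upward trend

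*SAP*

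**What the plan says.** SAP section 2.1.3.1 lists the endpoint as "Number of new T1 non-enhancing (hypointense) lesions (tertiary/exploratory"). The protocol's counterpart in section 3 (Table 6) is worded differently: "Change in the number of T1-hypointense lesions from Baseline over time".

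SAP section 2.4.4 sets out three summaries that matter here.

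- All lesion measures: "Number and volume of lesions will be summarized by visit using descriptive statistics in the mITT population including data from both DRI15928 and LTS16004".
- T2 counts, whether new or enlarging, are adjusted for the interval: "the values will be standardized to per month values by dividing by the number of months (4-week intervals) from the previous MRI". Such counts are also summarised as an "annualized rate of lesions (new/enlarging T2").
- New T1-hypointense counts are grouped with Gd-enhancing counts and summarised as an "average number of lesions per scan (new Gd-enhancing T1 hyperintense and new T1 non-enhancing hypointense").

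No time divisor or offset for new T1-hypointense lesions appears anywhere in the SAP.

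The comparison scan for these lesions is not clearly fixed. Protocol section 8.1.1 names the previous scan for Gd-enhancing and T2 lesions but does not mention T1-hypointense lesions. It then sets a default, subject to other specification, that "the baseline brain MRI will be used as the reference to assess all MRI derived endpoints".

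**The concern.** The SAP adjusts one count of new lesions for the scan interval and leaves a second count unadjusted. The documents treat T1-hypointense lesions, like T2 lesions, as a standing burden: both have a baseline count and a baseline volume (SAP 2.1.1), and both have volume endpoints (SAP 2.1.3.1). New members of a standing burden build up between scans, so a longer gap yields a larger count at the same rate.

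LTS16004 has no concurrent untreated arm, so change over time is the main thing a reader can take from its MRI data. SAP 2.4.4 allows graphs of time trends, and protocol section 2.1 gives as one goal to show that the MRI benefit persists. A plot of raw new T1-hypointense counts could suggest waning benefit when nothing has changed. It could also hide improvement: with a halved rate, the count at a 48-week gap would still be 0.5 × 4 = 2 times the earlier count at a 12-week gap.

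**Working it through.** The plan gives no expected lesion rate, sample size or power for this endpoint, so there is no figure of its own to reproduce. The check is arithmetic on the scan schedule.

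**Inputs**
- MRI visits: Day 1 and Months 3, 6, 12, 18, 24, 36, 48 and 60 (protocol section 1.3, Tables 1 to 3; the MRI column of SAP Table 2 has the same visits).
- One month is 28 days (protocol 1.3; SAP 2.5.3). Scans therefore fall at weeks 12, 24, 48, 72, 96, 144, 192 and 240 after Day 1.
- Gaps: 12, 12, 24, 24, 24, 48, 48 and 48 weeks.
- True rate: not given. Assume a constant r per week; it cancels in every ratio.

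**By-visit counts, previous scan as reference, lesions persisting**

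Expected count = r × gap, so the visits run 1 : 1 : 2 : 2 : 2 : 4 : 4 : 4. The largest ratio is 48/12 = 4.0.

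*Visit windows.* These are ±7 days in Year 1 and ±21 days for MRI from Month 15. A 12-week gap can be 84 ± 14 days and a 48-week gap 336 ± 42 days. The ratio then lies between 294/98 = 3.0 and 378/70 = 5.4.

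*Persistence.* If a lesion stays visible for only d weeks, the expected count is r × min(gap, d). With d = 24 the largest ratio is 24/12 = 2. With d of 12 or less it is 1. The full fourfold needs d of at least 48 weeks.

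**Average per scan, previous scan as reference, LTS16004 scans only**

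Average = r × (week of last scan) / (number of post-Day 1 scans).

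| Last scan | Weeks covered per scan | Full series ÷ this |
|---|---|---|
| Month 6 | 24/2 = 12 | 2.5 |
| Month 12 | 48/3 = 16 | 1.9 |
| Month 24 | 96/5 = 19.2 | 1.6 |
| Month 60 | 240/8 = 30 | 1.0 |

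*Group mean.* As an illustration, assume a share s of a group has the full series and the rest have a last scan at Month 6. The mean is 30s + 12(1 − s) weeks per scan: 22.8 for s = 0.6, 25.5 for s = 0.75 and 28.2 for s = 0.9. Two groups at 0.6 and 0.9 would differ by 28.2/22.8 = 1.24 at the same rate. Two groups with the same s would not differ.

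**Baseline as reference (counted from LTS16004 Day 1)**

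The by-visit count is then cumulative and does not depend on the latest gap. The average per scan, however, counts a persisting lesion again at every later scan. It is (12 + 24 + 48 + 72 + 96 + 144 + 192 + 240)/8 = 828/8 = 103.5 weeks of accrual for a full series and (12 + 24)/2 = 18 for a last scan at Month 6, a ratio of 5.75.

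**DRI15928 scans**

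The by-visit summaries include them, but the documents do not give their spacing. If it were 4 weeks (an assumption), the largest by-visit ratio would be 48/4 = 12. The averages above would also change.

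**After adjustment**

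Dividing each count by the time since the previous scan gives r at every visit. Total new lesions over total scan-to-scan time gives r for every length of follow-up. Under the same assumptions, all ratios become 1.0.

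**The case against.** The strongest reply is that little rests on this summary. The endpoint is tertiary/exploratory, SAP 2.4 rules out p-values, and the primary objective is safety. T1-hypointense lesion volume is also summarised by visit and does not depend on the scan interval in this way. All of this stands. It limits the importance of the point but does not remove the false trend.

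Four stronger readings are tempting, and the documents do not support them.

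- *That the per-scan average is inflated fourfold.* Fourfold is the ratio of single-visit counts. With the previous scan as reference, the average differs by at most 2.5-fold on the full LTS16004 schedule.
- *That the report will make participants who stay longer look worse than those who leave early.* Summaries are by dose group and overall; none is by length of stay. Stopping treatment is also not the same as stopping scans: protocol section 7.1.1 keeps such participants under study procedures, and an MRI is scheduled at premature end of treatment. The ratios in the table above compare scan series. They do not estimate bias in a reported mean.
- *That dose-group comparisons are biased.* All groups share one schedule. Distortion needs different follow-up or missed scans between groups, and the documents give no evidence of either.
- *That with baseline as reference the by-visit rise would be an artefact too.* It would be real accumulation, close to the protocol's own endpoint. Only the per-scan average misleads in that case.

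The SAP does not say why T2 counts are standardised, nor whether the per-scan average is taken per participant or over pooled scans. The case here rests on the arithmetic, not on an inferred motive.

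**Conclusion.** The point holds as a modest inconsistency worth correcting. With the previous scan as reference, a constant rate and lesions that persist across the gaps, by-visit counts rise fourfold between the 12-week-gap and 48-week-gap visits. The per-scan average then varies up to 2.5-fold with the set of scans contributed, on LTS16004 scans alone. If lesions resolve sooner, the effect is smaller. It disappears only if they last no longer than the shortest gap, and nothing in the documents says so. Including DRI15928 scans would change the averages by an amount that cannot be worked out from the documents.

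If baseline is the reference, the by-visit count is sound and the fault is confined to the per-scan average. The average per scan is therefore hard to interpret under either reference. The damage is to the time trend and the pooled average of a descriptive, exploratory endpoint. The primary safety analysis and the secondary endpoints are not affected, and the point makes no claim about Gd-enhancing counts.

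**What to change.** In SAP section 2.4.4:

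1. Name the previous MRI as the reference for new T1-hypointense lesions.
2. Divide each by-visit count by the number of 4-week months since that MRI, using actual scan dates.
3. Replace their per-scan average with an annualised rate, on the same convention as for new/enlarging T2 lesions.
4. Keep the per-scan average for Gd-enhancing lesions only.

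The cost is a sentence or two in the SAP and a small programming change that reuses the T2 derivation. The scan dates are already needed for T2 lesions, so no new data are required.
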